5.1 Investigational treatment

The investigational drug, MCS110, will be prepared by Novartis and supplied to the Investigator as open labeled bulk medication.

- Name: MCS110
- Formulation: Liquid in Vial (Concentrate for solution for infusion)
- Unit dose: MCS110 150MG Liquid in vial 7.5ML

5.1.1 Bio-batch Retention samples

Not applicable.

5.2 Treatment arms

5.2.1 Part A

Patients will be assigned to one of the following 2 treatment arms in a ratio of 2:1 MCS110 to placebo.

5.2.2 Part B

For the first dose, patients will be assigned to one of the following 2 treatment arms in a ratio of 2:1 MCS110 to placebo. All patients from the second and subsequent doses will receive MCS110 in open label.

5.2.3 Part C

Approx. 15 patients (including adults and adolescents $\geq 12 - \langle 18 \rangle$ years old) will be randomized in double-blind manner to one of the following 3 parallel arms: 3 mg/kg or 5 mg/kg or 10 mg/kg of MCS110 in a ratio of approximately 2:2:1.

In case a lower dose is identified to be at least as efficacious as 10 mg/kg after 3 doses, additional 4 patients may be enrolled in this lower dose group and randomized in an open label fashion to a total of approximately 10 patients.

Table 5-1 Treatment arms in Part C

Treatment	Double-blind	Potential open label extension
3 mg/kg	n ~6	n ~4*
5 mg/kg	n ~6	n ~4*
10 mg/kg	n ~ 3	n=0

*Either 3 or 5 mg/kg may be expanded.

5.3 Treatment assignment

Treatment / randomization numbers will be assigned in ascending, sequential order to eligible patients in accordance with entry into the study. The treatment / randomization number becomes the definitive patient number as soon as a patient receives the first dose of the respective study treatment.

The investigator will enter the randomization number on the CRF (eCRF). The randomization numbers will be generated using the following procedure to ensure that treatment assignment is unbiased and concealed from patients and investigator staff. A randomization list will be produced by or under the responsibility of Novartis Drug Supply Management using a validated system that automates the random assignment of treatment arms to randomization numbers in the specified ratio. The randomization scheme for patients will be reviewed and approved by a member of the Biostatistics Quality Assurance Group.

When an eligible patient at a study site requires randomization into the study, the study nurse or the unblinded pharmacist/designee at the study site will complete an application to the assigned randomization coordinator who will then issue a randomization number. The unblinded pharmacist/designee will then ensure that the correct study medication is prepared, according to the corresponding Treatment Allocation Card of the assigned randomization number. Full details of this process are documented in the Randomization Manual.

Confidential

5.4 Treatment blinding

Part A and first dose Part B

This is a double blind study: patients, investigator staff (except the unblinded pharmacist), persons performing the assessments, and data analysts will remain blind to the identity of study treatments according to the specifications provided in Appendix 2.

A safety review will be carried out after each patient completes the 4-week treatment period, therefore the independent safety reviewer will be unblinded on an ongoing basis.

Randomization data are kept strictly confidential until the time of unblinding for the respective person(s). Further information regarding blinding and unblinding is presented in Appendix 2. The identity of the treatments will be concealed by the use of study drugs that are all identical in packaging, labeling, schedule of administration and appearance. Unblinding will only occur in the case of patient emergencies (see Section 5.5.10), at the time of the interim analysis and at the conclusion of the study.

Part B

Double-blind study part will be followed by an open label part from the second to the sixth dose.

Day 1 treatment will be maintained double blinded until week 12. At week 12, Day 1 treatment will be un-blinded in order to allow Day 1 placebo patients to receive two more MCS110 doses in open label.

Part C

28 weeks double-blind treatment period study part will be followed by an open label part.

Day 1 treatment will be maintained double-blinded until primary endpoint reached at Week 28 (or until any premature primary endpoint) to the Novartis clinical team and the investigator.

Following week 12 MRI, Novartis independent statistician (independent from the clinical study team) will proceed to the un-blinding and will share allocated dose level with an unblinded Novartis medical person (independent from the clinical team) who will review patient's safety profile and tumor volume reduction. The unblinded medical person will determine if the patient fulfills dose change conditions. The site's unblinded pharmacist will be informed by an independent study team member of potential dose change.

5.5 Treating the patient

5.5.1 Patient numbering

Screening number

Each patient screened is assigned a unique screening number. The screening number is a combination of the center number that is provided by Novartis, and a four digit number starting with 0001 for each patient which is assigned by the Investigator. Therefore, if the center number is 3001 (any leading 0's in the center number are dropped) the screening numbers will be assigned such as 3001_0001, 3001_0002, 3001_0003 in ascending order. If the center number is 3002, the screening numbers will be 3002_0001, 3002_0002, 3002_0003 in an ascending order.

Randomization / treatment number

If the patient is deemed eligible for enrollment into the study and will commence dosing, a randomization/ treatment number will be assigned. Once assigned to a patient, a treatment number or randomization number will not be reused.

There should be a source document maintained at the site which links the screening number to the randomization / treatment assignment number (once assigned). Patients will be assigned treatment numbers, 5101-5118. Replacement patients will be assigned treatment numbers, 6101-6118. If a patient requires a replacement, the replacement patient will be assigned a treatment number corresponding to the original patient (e.g., Patient 6103 would replace Patient 5103).

In Part C, patients will be assigned treatment numbers, 5119-5148, and potentially 5150–5158, if arm extension is done for the efficacious lower dose. Replacement patients will be assigned treatment numbers, 6119-6148; 6150-6158. If a patient requires a replacement, the replacement patient will be assigned a treatment number corresponding to the original patient (e.g., Patient 6120 would replace Patient 5120). The randomization numbers 5149 and 6149 are not going to be used in the study Part C.

The Table 5-2 details the general details of the numbering of the patients once assigned / randomized to treatment:

5		
Arm	Randomization numbers	Replacement randomization numbers
l (n=18)	5101 – 5118	6101 – 6118
II (n=30)	5119 - 5148	6119 - 6148
III (n=8: potential extended arm)	5150 – 5158	6150 - 6158

Table 5-2 Treatment Assignment Numbering

5.5.2 Dispensing the study treatment

For preparation of the study medication, a copy of the treatment allocation cards will be sent to the pharmacist / technician at the Investigator's site.

Appropriate documentation of the patient specific dispensing process must be maintained.

Bulk medication labels will be in the local language, will comply with the legal requirements of each country, and will include storage conditions for the drug but no information about the patient.

5.5.3 Supply, storage and tracking of study treatment

Study drugs must be received at the study site by a designated person, handled and stored safely and properly, and kept in a secured location to which only the Investigator and designated staff have access. Upon receipt, the study drugs should be stored according to the instructions specified on the drug labels.

Storage conditions must be adequately monitored and appropriate temperature/humidity logs maintained as Source data.

The Investigator must maintain an accurate record of the shipment and dispensing of study drug in a drug accountability ledger. Drug accountability will be verified by the Monitor during site visits and/or at the completion of the trial.

All drug supplies are to be used only for this protocol and not for any other purpose. Unless specifically instructed by Novartis, the Investigator must not destroy any drug labels, or any partly used or unused drug supply.

At the conclusion of the study, and, if allowed during the course of the study (e.g., an open label study or an un-blinded monitor), the Investigator will provide a copy of the drug accountability ledger to the Monitor.

Only after receiving a written authorization by Novartis, the Investigator/designee will send all the unused and partly used drug supplies as well as the empty containers to the address provided at the time of authorization for destruction or have the unused and partly used drug supplies as well as the empty containers destroyed by the site's pharmacist, providing a drug destruction certificate.

5.5.4 Instructions for prescribing and taking study treatment

Part A and first dose Part B

A single dose of MCS110 at 10 mg/kg will be administered on day 1. Patient dosing should occur within 7 days after validated reference MRI was performed.

Part B from dose 2 to dose 6:

A single dose of MCS110 at 10 mg/kg will be administered on weeks 4, 8, 12, 16, and 20. Patient dosing should occur after follow-up MRI was performed.

Part C from dose 1 to 6:

A single dose of treatment (3, 5 or 10 mg/kg) will be administered on Day 1 and weeks 4, 8, 12, 16, and 20. Patient dosing should occur after follow-up MRI was performed.

Part A, Part B and Part C

Administration will be by regular infusion (gravity or pump assisted). The intravenous infusion will last for 1 hour ± 10 minutes. The dose will be calculated from the individual patients' body weight as measured at the baseline visit and subsequent visits prior to the administration. The infusion duration is based on safety consideration, as it allows termination of infusion in case immediate adverse events arise.

The patient should be monitored in the clinic for 4 hours from the end of dosing. The study medication preparation guidelines are described in the Dose Preparation and Administration Manual.

During the MCS110 infusion, the patient's vital signs (blood pressure, pulse, respiration and temperature) will be monitored every 15 ± 5 minutes for the duration of the infusion and at the time of discontinuation of the infusion. In addition, vital signs will be monitored post infusion.

The infusion should be slowed or stopped and the responsible physician notified immediately should any of the following conditions apply:

- 1. Systolic blood pressure is more than 20 mm Hg above or below baseline (Note: If blood pressure drops \geq 30 mm Hg, the infusion should be stopped immediately).
- 2. Pulse is more than 20 beats per minute above or below baseline or if pulse is irregular.
- 3. Temperature is $> 38.5^{\circ}$ C.
- 4. There are other clinical signs or symptoms of a hypersensitivity or infusion reaction (e.g., rigors, dyspnea, hypoxia and wheezing).

In addition, the drug infusion may be stopped at any time at the discretion of the investigator for an adverse event of lesser severity.

In case of an infusion reaction appropriate treatment should be administered as described in Table 5-3 and in Table 5-4. If infusion reactions symptoms have improved after interruption, the infusion can be resumed at one-half of the previous rate. The rate of infusion can only be reduced twice.

All dosages prescribed and dispensed to the patient and all dose changes during the study must be recorded on the Dosage Administration Record CRF (eCRF).

5.5.5 Permitted dose adjustments and interruptions of study treatment

5.5.5.1 Part A

If $CK > 5 \times ULN$ occurs in 2 patients, subsequent patients may be treated with a lower dose. Such a change will be implemented via an amendment to the protocol.

In the event of a severe infusion reaction, the investigator should stop the infusion of MCS110 immediately and the patient must be discontinued from the study (Table 5-3).

Table 5-3 Criteria for addressing infusion/hypersensitivity reactions in Part A

Confidential

Allergy/Immunology	Action
Infusion-related reaction / hypersensitivity	Maintain dose level.
Flushing; rash; urticaria; dyspnea; drug	Immediately stop MCS110 infusion and discontinue
fever ≥38.5°C/≥101.3°F or symptomatic	patient from study.
bronchospasm, with or without	Medication such as anti-histamines or corticosteroids
urticaria ^a ; allergy-related	should be given for symptomatic relief. Epinephrine can
edema/angioedema; hypotension	be indicated when wheezing and anaphylaxis of acute
(characterized by a systolic pressure	life-threatening nature is present but should be chosen
drop ≥ 30 mm Hg) or anaphylaxis ^b	cautiously.

^a Urticaria with manifestations of allergic or hypersensitivity reaction is graded as Allergic reaction/hypersensitivity.

^{b.} Anaphylaxis is defined as vascular collapse and shock (blood pressure < 90 mm Hg that is unresponsive to IV fluids) believed to be allergic in origin, with or without antecedent respiratory distress and occurring within 30 minutes of initiation of MCS110 infusion. Cutaneous manifestations include pruritus, urticaria, or angioedema.

5.5.5.2 Part B and Part C

Dosing adjustment due to safety issues / adverse events

In the event of a severe infusion reaction, the investigator should stop the infusion of MCS110 immediately and the patient must be discontinued from the study (Table 5-2).

Patients may receive pre-medication before the first infusion [anti-histamine (diphenhydramine 50 mg or equivalent) and acetaminophen (1 g)].

Table 5-4	Criteria for addressing infusion/hypersensitivity reactions in Part B/C
-----------	-------------------------------------------------------------------------

Toxicity	Action
CTCAE grade (value)	
Infusion-related reaction/ hypersensitivity	
Grade 1:	Maintain dose level.
transient flushing or rash, drug fever <38°C/ < 100.4°F	May premedicate at subsequent infusions with anti-histamine (diphenhydramine 50 mg or equivalent) and acetaminophen (1 g). Patients must then be observed for at least 3 hours after each subsequent infusion before being discharged from the treatment center.
Grade 2: flushing, rash, urticarial, dyspnea, drug fever ≥38.5°C/≥101.3°F	Interrupt the infusion of MCS110, administer anti-histamines or corticosteroids to be given for symptomatic relief. After recovery of symptoms, resume the infusion at a slower rate (50% of previous rate) and, if no further symptoms appear, complete the administration of the dose.
Toxicity	Action
CTCAE grade (value)	
Grade 3: symptomatic bronchospasm, with	Immediately stop MCS110 infusion and discontinue patient from study.
or without urticaria ^a ; allergy-related edema/angioedema; hypotension (characterized by a systolic pressure drop ≥ 30 mm Hg)	Medication such as anti-histamines or corticosteroids should be given for symptomatic relief.
Grade 4:	Immediately stop MCS110 infusion and discontinue
anaphylaxis ^b	patient from study.
	Epinephrine can be indicated when wheezing and anaphylaxis of acute life-threatening nature is present but should be chosen cautiously.

^{a.} Urticaria with manifestations of allergic or hypersensitivity reaction is graded as Allergic reaction/hypersensitivity.

^{b.} Anaphylaxis is defined as vascular collapse and shock (blood pressure < 90 mm Hg that is unresponsive to IV fluids) believed to be allergic in origin, with or without antecedent respiratory distress and occurring within 30 minutes of initiation of MCS110 infusion. Cutaneous manifestations include pruritus, urticaria, or angioedema.

If a patient develops periorbitalswelling, subsequent dosing (e.g., 4 wks, 8 wks) will be put on hold until one week after the swelling has resolved.

If a patient develops any adverse event considered as drug related by the investigator, which has not resolved before the following dose, next dosing will be delayed until considered resolved.

If there are abnormal hematology and / or biochemistry laboratory values (CTCAE grade 3) judged as clinically significant by the Investigator, the next dose will be delayed until abnormalities have resolved. Isolated CK increase with normal troponin T and aldolase is not considered a safety concern even if reaching CTCAE grade 3.

Part B: If dosing of 4 times 10 mg/kg MCS110 (once every 4 weeks) is exceeding the initial 13 weeks dosing period, (due to occurrence of AEs) further dosing will be allowed up to week 20 if all AEs had resolved for more than a week and efficacy assessment demonstrates response to treatment (>50 % of tumor volume reduction after 3^{rd} dose in Part B, 45% in Part C) of these patients.

Dosing extension to 6 consecutive doses once every 4 weeks

Patients initially receive 4 consecutive doses once every 4 weeks (week 0, 4, 8, 12). Patients will receive 1 or 2 additional doses under the following conditions:

- no treatment related safety issues (for periorbital swelling* only if >grade 2) resulting in dosing delay during the first 4 doses the tumor has not been completely eliminated after the 3rd dose [determined by MRI at week 12]
- the tumor did respond to treatment (Part B: >50 % tumor volume reduction) after the 3rd dose [determined by MRI at week 12] Corporate Confidential Information

In Part C additional criteria apply as following:

- Part C (arms 3 mg/kg or 5 mg/kg): the tumor did respond to treatment (≥45 % tumor volume reduction) after the 3rd dose [determined by MRI at week 12] and MCS110 was tolerated: the patient will receive 3 additional doses of the same as dose level
- Part C (arms 3 mg/kg or 5 mg/kg): the tumor response to treatment is <45 % of tumor volume reduction after the 3rd dose [determined by MRI at week 12] and MCS110 was tolerated: the patient will receive doses increased to 10 mg/kg
- Part C (arm 10 mg/kg): the tumor did respond to treatment (≥45 % tumor volume reduction) after the 3rd dose [determined by MRI at week 12] and MCS110 was tolerated: the patient will receive 3 additional doses of 10 mg/kg
- Part C (arm 10mg/kg): the tumor response to treatment is <45 % of tumor volume reduction after the 3rd dose [determined by MRI at week 12] and MCS110 was tolerated: the patient can receive 1 additional dose of 10 mg/kg

New treatment course in case of recurrence of tumor or regrowth of residual tissue

If, based on MRI, relapse is identified, it is possible to start an additional course of 6 consecutive doses of MCS110 10 mg/kg, if there was:

- Good tolerability of MCS110 during the first treatment cycle
 - Patient received 6 doses
 - No early treatment discontinuation

- Good response in tumor volume reduction: Tumor volume reduction at (up to) 1°EP (8 wks post last dose of 6 doses) of >50% during the 1st treatment cycle
- Relapse defined as:
 - Symptoms (pain, swelling, redness, stiffness) and
 - Tumor volume increase greater than 50% of the difference between tumor volume at BL and the lowest tumor volume measured by MRI.
- Last dose of MCS110 was at least \geq 6 months ago.
- Inclusion/exclusion criteria are still fulfilled.

During the second treatment course safety monitoring will be the same as during the first treatment course. Efficacy will be assessed by MRI after the 3rd dose at week 12 to decide on dosing beyond 4 doses and then again 8 weeks post last dose. Once a lower dose with same efficacy as 10 mg/kg has been identified in Part C, relapse patients will receive the lower dose treatment. During the second treatment course no placebo dose will be administered.

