3.5.2 Possible study related risk

Risk of infusion reaction: In CMCS110A2101, of the 3 patients treated, one patient treated with MCS110 at the 0.01 mg/kg dose level experienced an infusion related reaction characterized by transient chills, hypotension, and dizziness 1 hour after completing the first MCS110 infusion with all 3 adverse events resolved approximately 1 hour after occurrence. The 2 other patients treated with MCS110 did not experience infusion reaction. Consequently, patients with a history of infusion reactions to, e.g., antibody treatment will be excluded.

In the ongoing part C (cut-off date: 19-Jan-2018) 5 patients experienced an infusion reaction, 4 of them during or directly after the first dose of MCS110. Two of the infusion reaction cases were classified as SAEs, but in both patients the infusion reactions resolved quickly after the administration of fluid and medications. Patients may receive pre-medication before the first infusion.

Risk from being exposed to radiation: This clinical study involves exposure to radiation Corporate Confidential Information (Part

B: 3 times, optional; Part C: 2 times). Corporate Confidential Information

Corporate Confidential Information

Risk from taking a biopsy by arthroscopy or via percutaneous needle: these methods are used in the diagnosis and treatment of disease or abnormalities of joints, including PVNS. It is possible, though unusual, to experience a bleeding episode during or after surgery or after a needle biopsy. This may require emergency treatment to drain accumulated blood. An infection risk is rare, but in case an infection occurs, treatment including antibiotics or additional surgery may be necessary. There may be temporary stiffness, swelling and pain after the procedure. There may be damage to the surrounding nerves or tendons. There may be the potential to develop an allergic reaction to tape, suture material, or topical preparations, which may require additional treatment.

Risk assessment for effects of MCS110 on bone parameters in skeletally mature patients with PVNS and their extrapolation to the immature skeleton:

Corporate Confidential Information

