5.5.7 Concomitant treatment

The investigator should instruct the patient to notify the study site about any new medications he/she takes after the start of the study drug. All medications and significant non-drug therapies (including physical therapy and blood transfusions) administered after the patient starts treatment with study drug must be listed on the Concomitant medications/Significant non-drug therapies after start of study drug eCRF.

All prescription medications and over-the-counter drugs taken within the timeframe defined in the entry criteria prior to the start of the study and during the study, must be recorded on the Concomitant Medications/ Non-Drug Therapies page of the eCRF.

Medication entries should be specific to trade name, the single dose and unit, the frequency and route of administration, the start and discontinuation date and the reason for therapy.

Allowed medication

- Adjuvant radiation therapy as clinical standard of care after surgery (only for Part A).
- Patients on treatment with cholesterol lowering medication or anti-hypertensives can continue with their medication, but it must be documented in the Concomitant medications / Significant non-drug therapies page of the eCRF.
- Diabetes drugs (in Part C)
- If needed, paracetamol / acetaminophen and NSAIDs (Non-Steroidal Anti-Inflammatory Drugs) are acceptable, but must be documented in the Concomitant medications / Significant non-drug therapies page of the eCRF. NSAIDs must be discontinued prior to surgery according to local practice. All pain medication must be discontinued 24h prior to QoL questionnaires assessments at time-points according to Assessment Schedule.

• Patients may receive pre-medication before the first infusion [anti histamine (diphenhydramine 50 mg or equivalent) and acetaminophen (1 g)] or patients with mild infusion reactions, may premedicate at subsequent infusions with anti-histamine (diphenhydramine 50 mg or equivalent) and acetaminophen (1 g). Patients must then be observed for at least 3 hours after each subsequent infusion before being discharged from the treatment center.

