5.5.9 Discontinuation of study treatment and premature patient withdrawal

Study "Stopping rules"

The study will be put on hold and no further dosing will be taken pending a full safety review, if any of the following criteria are met:

- 1. 1 or more study-drug related SAEs are reported.
- 2. At least 2 patients in the active arm experience a similar AE which is assessed as either moderate or severe in intensity, and is potentially related to study-drug. Periorbital edema that resolves will not lead to study cessation, as noted above.
- 3. Only Part A: CK > 5 x ULN (CTCAE grade 3) (CTCAE, version 4.0) occurs in 2 patients on active treatment.

Individual patient withdrawal

Part A

As this is a single dose study, treatment interruption will occur only if there is evidence of an infusion reaction during study drug administration (Table 5-3).

Parts A, Part B and Part C

Patients or legal representatives may voluntarily withdraw from the study for any reason at any time. They may be considered withdrawn if they state an intention to withdraw, fail to return for visits, or become lost to follow-up for any other reason. If premature withdrawal occurs for any reason, the investigator must make every effort to determine the primary reason for a

patient's premature withdrawal from the study and record this information on the Study Completion eCRF.

Confidential

Part B and Part C

The investigator should discontinue study treatment for a given patient or withdraw the patient from the study if, on balance, he/she believes that continuation would be detrimental to the patient's well-being.

Treatment interruption will occur if there is evidence of an infusion reaction during study drug administration (Table 5-4) or any other adverse event which in the opinion of the investigator warrants discontinuation of the infusion.

Discontinuation of study treatment and patient withdrawal will be at the discretion of the Investigator, under the following circumstances:

- Infusion-related adverse event, such as hypotension, rash, or other evidence of an infusion reaction while the infusion is still running.
- Any other protocol deviation that results in a significant risk to the patient's safety.

Study treatment must be discontinued and the patient withdrawn from the study if one the following occurs:

- Patient or the legal representative withdraws consent
- Pregnancy
- Severe hypersensitivity reaction
- Drug-related SAE

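### In Parts B and C the infusion-reaction rules give different dispositions for the same fall in blood pressure, cite the wrong table, state two minimum observation times and leave gaps in Table 5-4

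*Protocol*

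**What the plan says.** Five places in the protocol govern an infusion reaction in Parts B and C.

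- **Section 5.5.4 (all Parts).** A systolic fall of 30 mm Hg or more calls for an immediate stop of the infusion. Reactions are to be treated as in Tables 5-3 and 5-4. The next sentence reads: "If infusion reactions symptoms have improved after interruption, the infusion can be resumed at one-half of the previous rate". On observation: "The patient should be monitored in the clinic for 4 hours from the end of dosing".
- **Section 5.5.5.2, opening text.** A severe infusion reaction requires discontinuation from the study. The table cited is 5-2.
- **Section 5.5.5.2, Table 5-4.** Hypotension with a systolic fall of 30 mm Hg or more is grade 3: stop the infusion and take the patient out of the study. The grade 1 row allows premedication at later infusions and adds "Patients must then be observed for at least 3 hours after each subsequent infusion before being discharged from the treatment center". Drug fever is grade 1 below 38°C and grade 2 from 38.5°C. Footnote b restricts anaphylaxis, which is the grade 4 row, to shock "occurring within 30 minutes of initiation of MCS110 infusion".
- **Section 5.5.7.** The 3-hour text is repeated in a bullet on premedication, where "patients with mild infusion reactions, may premedicate at subsequent infusions with anti-histamine".
- **Section 5.5.9 (Parts B and C).** "Discontinuation of study treatment and patient withdrawal will be at the discretion of the Investigator, under the following circumstances". The first circumstance listed is an infusion-related event, with hypotension as an example, while the infusion is running. A separate mandatory list names a severe hypersensitivity reaction and a drug-related SAE.

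**The concern.** A site managing an acute reaction can follow one section and breach another. The conflict also decides who stays in the trial. Table 5-4 removes the patient from the study, whereas 5.5.9 sends patients who stop treatment early on to follow-up. So the MRI 8 weeks after the last dose, which is the Part C primary endpoint, may or may not be collected depending on which section is applied.

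The arms are small enough for one patient to matter. Table 5-1 plans about 6, 6 and 3 patients, so one patient is about 17% (1/6) or 33% (1/3) of an arm. The Part C replacement rule in 5.5.9 covers only withdrawals for reasons other than safety, although Section 4 leaves replacement of non-evaluable patients to the sponsor. SAP Section 7.1.1 does not impute missing data.

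**Working it through.** No sample size, power or error rate is involved, so the check sets the texts side by side.

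**1. A systolic fall of 30 mm Hg or more during the infusion (Parts B and C)**

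| Source | Infusion | Patient's place in the study |
|---|---|---|
| Table 5-4, grade 3 | Stop at once | Discontinued, no discretion |
| 5.5.9, discretionary list | Not stated | Investigator decides; no size or grade limit on hypotension |
| 5.5.4 | Stop at once; improved reactions may resume at half rate after interruption, with no grade limit | Not stated |

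Two dispositions are stated, mandatory and discretionary, and one source is silent.

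**2. Cross-reference.** The severe-reaction sentence in 5.5.5.2 points to Table 5-2. That table (Section 5.5.1) lists randomization numbers. The reaction criteria for Parts B and C are in Table 5-4, which 5.5.9 cites correctly for interruption.

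**3. Observation times.** Section 6 counts time from the start of dosing. Section 5.5.4 gives an infusion of 1 hour ± 10 minutes.

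- 3-hour minimum: 1 h + 3 h = 4 h after the start (3 h 50 min to 4 h 10 min).
- 4-hour monitoring: 1 h + 4 h = 5 h after the start (4 h 50 min to 5 h 10 min).
- Difference between the two: 4 h − 3 h = 1 h.
- Interval from the 3-hour minimum to the 5-hour time point: 5 h − 4 h = 1 h (50 to 70 min).

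The Part B and C schedules list vital signs at 5 hours on dosing days; the Part B schedule also lists PK and total M-CSF samples then. Section 6 gives samples after Day 1 a window of ± 6 hours, so those samples could formally be drawn before an earlier discharge. That window is stated for samples, not for vital signs.

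**4. Gaps in Table 5-4.** With grade 1 below 38°C and grade 2 from 38.5°C, temperatures of 38.0-38.4°C have no row. Footnote b covers the first 30 of the 60 planned infusion minutes; shock after that does not meet the grade 4 definition as written. It would usually meet the grade 3 pressure criterion instead. The footnote uses a pressure below 90 mm Hg, and 90 + 30 = 120. From a baseline below 120, a pressure just under 90 is therefore a fall of less than 30, and such a case would rest on the severe-reaction wording. Grades 3 and 4 both end in stopping and discontinuation from the study, so the disposition would probably be the same either way.

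**5. Scale.** Section 3.5.2 reports for Part C that "5 patients experienced an infusion reaction, 4 of them during or directly after the first dose of MCS110", and that two cases were SAEs. The introduction's account of this study gives 18 patients exposed in Part C. 5/18 = 27.8% (Clopper-Pearson 95% CI 9.7% to 53.5%).

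**The case against.** Much of this can be read in harmony. The discretionary item in 5.5.9 names hypotension without a figure. Section 5.5.4 also has a lower trigger, a change of more than 20 mm Hg, so the item may be meant for smaller falls, with grade 3 events under the mandatory list. The half-rate sentence in 5.5.4 follows directly on the reference to the tables and matches the grade 2 action. That reading is reasonable, but no section states it. The introduction labels grade 1 mild and grade 2 moderate, yet nothing says that grade 3 is what 5.5.5.2 and 5.5.9 mean by severe.

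Four stronger readings are tempting and are not supported.

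- **That patients who have reacted are to be watched for less time than everyone else.** The 3 hours are a floor, the 4-hour rule exempts nobody, and 4 hours satisfies both. The 3-hour text covers premedicated patients, chiefly those with a mild earlier reaction; in 5.5.7 it arguably also covers premedication before a first infusion. The grade 2 row gives no separate time.
- **That some section lets a patient with a 30 mm Hg fall continue without discontinuation.** No section says so. Section 5.5.4 is silent on the patient's status and orders a stop.
- **That late anaphylaxis would be missed.** The first-in-human patient had moderate hypotension 1 hour after the infusion ended, and it resolved in about 1 hour. Nothing there describes shock. The case shows only that onset can be late.
- **That 28% measures the conflict.** It counts all Part C infusion reactions. The documents do not say that any involved a 30 mm Hg fall or fell under conflicting rules.

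**Conclusion.** The concern holds for Parts B and C in four limited respects.

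1. Table 5-4 and 5.5.9 disagree on whether discontinuation is mandatory for hypotension during the infusion, and 5.5.4 adds a permission to resume that is not limited by grade. This is the main point.
2. The compulsory rule for severe reactions cites the wrong table.
3. The stated minimum observation times differ by 1 hour. They are compatible, but the lower one ends about 1 hour before the 5-hour assessments.
4. Table 5-4 has no row for 38.0-38.4°C and leaves the class of later-onset shock unclear, probably without changing the disposition.

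The number of patients affected cannot be derived from the documents. The 5 of 18 shows only that infusion reactions were not rare in Part C, and it assumes that the reaction count and the exposure count refer to the same patients. The timing in point 3 assumes an infusion at the planned rate. No view is taken on which clinical rule is right.

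**What to change.** Reconcile Sections 5.5.4, 5.5.5.2 (with Table 5-4), 5.5.7 and 5.5.9:

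- Give each Table 5-4 grade one disposition, saying whether treatment alone or study participation ends. Make the resumption text in 5.5.4 and the discretionary list in 5.5.9 expressly subject to the table.
- Correct the reference to Table 5-2 in 5.5.5.2 to Table 5-4.
- Reconcile the two observation times with each other and with the 5-hour assessments.
- State how drug fever of 38.0-38.4°C and shock arising after the footnote b window are classified.

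The sponsor's medical team should decide the clinical content of each item. The cost is protocol wording; any change in clinic time depends on how the observation times are reconciled.
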